### **7.1 Schedule of Assessments**

**Table 1. Schedule of Assessments**

Weeks	30-day Screening	Treatment Period								Disease Assessment (DA)		30-day Follow-Up Safety (EOS) 
		0 (day 1)	4	8	12	16	24	36	48/ET	DA Visit e	DA Follow-up e	
GENERAL & SAFETY ASSESSMENTS												
Informed consent	X											
Randomization via IXRS		X										
Medical/Medication history	X											
Concomitant medications		X	X	X	X	X	X	X	X	X	X	
Adverse events		X	X	X	X	X	X	X	X	X	X	
Serious adverse events	X	X	X	X	X	X	X	X	X	X	X	X
Physical examination a	X	X			X		X	X	X	X	X	
Vital signs	X	X	X	X	X	X	X	X	X	X	X	
Weight	X	X							X	X	X	
Height	X											
LABORATORY ASSESSMENTS												
Pregnancy test (serum) b	X											
Pregnancy test (urine) b,c		X			X		X	X	X			
Tuberculosis testing d	X											
Hematology and chemistry profile	X		X	X	X		X	X	X	X	X	
Hepatitis B surface antigen & core antibody; Hepatitis C virus antibody f	X											
High Sensitivity C-reactive Protein		X	X	X	X	X	X	X	X	X	X	
Urinalysis	X								X			
Biomarker blood sample		X		X			X		X			
INVESTIGATIONAL PRODUCT DISPENSING												
Etanercept/placebo for etanercept dispensation		X	X	X	X		X	X		X g	X	
Methotrexate/placebo for methotrexate dispensation		X	X	X	X		X	X		X g	X	
Folic Acid h		X			X		X	X				
SUBJECT DIARY DISPENSING												
Dispense subject diary		X	X	X	X	X	X	X				
Review subject diary			X	X	X	X	X	X	X	X	X	
DISEASE ASSESSMENTS												
Swollen and Tender joint count	X	X	X	X	X	X	X	X	X	X	X	
Physician Global Assessment of Disease Activity (VAS 0 to 100)		X	X	X	X	X	X	X	X	X	X	
Leeds Dactylitis Index		X	X		X		X	X	X	X	X	
Spondyloarthritis Research Consortium of Canada (SPARCC) Enthesitis Index		X	X		X		X	X	X	X	X	
Modified Nail Psoriasis Severity Index (NAPSI)		X	X		X		X	X	X			
Static Physician Global Assessment of Psoriasis		X	X		X		X	X	X	X	X	
Body Surface Area		X	X		X		X	X	X	X	X	
Radiographs (hands, feet)		X					X		X			

Footnotes defined on next page

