## 7.2 General Study Procedures

The procedures performed at each study visit are outlined above in [Table 1](#). Details regarding each type of procedure are provided in subsequent sub-sections.

Refer to the applicable supplemental central laboratory, IXRS, IPIM, and study manuals for detailed collection and handling procedures.

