#### **7.3.8.3 Spondyloarthritis Research Consortium of Canada Enthesitis Index**

Assessment will be performed by the same assessor as the joint counts. The assessor will be trained by viewing the GRAPPA training module to perform the Spondyloarthritis Research Consortium of Canada (SPARCC) enthesitis assessment. The SPARCC enthesitis index assesses enthesitis at 18 sites with a resultant score of 0 to 16.

Tenderness at each site is assessed as 0 = non-tender or 1 = tender. Enteses assessed are left and right medial and lateral epicondyles, supraspinatus insertion into greater tuberosity of humerus, greater trochanter, quadriceps insertion into superior border of patella, patellar ligament insertion into inferior pole of patella, tibial tubercle, Achilles tendon insertion into calcaneum and bilateral plantar fascia insertion into the calcaneum. Higher count represents greater enthesitis burden. Tenderness at the inferior pole of patella and/or tibial tubercle will be scored as a maximum score of 1.

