##### 10.1.1.3 Other Secondary Endpoints

- Modified NAPSI score and change from baseline at week 24
- Leeds dactylitis score and change from baseline at week 24
- SPARCC enthesitis score and change from baseline at week 24
- ACR 20 response at all other measured timepoints
- MDA response at all other measured timepoints
- Psoriatic Arthritis Disease Activity Score (PASDAS) at all measured timepoints
- ACR 50, ACR 70, and components of ACR at all measured timepoints

- Simplified Disease Activity Index (SDAI) and change from baseline at all measured timepoints
- Clinical Disease Activity Index (CDAI) and change from baseline at all measured timepoints
- Disease activity score (28 joint) using the C-reactive protein formula (DAS28-CRP) and change from baseline at all measured timepoints
- HAQ-DI score and change from baseline at week 24
- SF-36 score and change from baseline at week 24

For subjects with involved BSA  $\geq 3\%$  at baseline:

- sPGA at week 24
- BSA at week 24

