## **12. ADMINISTRATIVE AND LEGAL OBLIGATIONS**

### **12.1 Protocol Amendments and Study Termination**

If Amgen amends the protocol, agreement from the Investigator must be obtained. The IRB/IEC must be informed of all amendments and give approval. The investigator must send a copy of the approval letter from the IRB/IEC to Amgen.

Amgen reserves the right to terminate the study at any time. Both Amgen and the Investigator reserve the right to terminate the Investigator's participation in the study according to the study contract. The investigator is to notify the IRB/IEC in writing of the study's completion or early termination and send a copy of the notification to Amgen. Subjects may be eligible for continued treatment with Amgen investigational product(s) by an extension protocol or as provided for by the local country's regulatory mechanism. However, Amgen reserves the unilateral right, at its sole discretion, to determine whether to supply Amgen investigational product(s) and by what mechanism, after termination of the study and before the product(s) is/are available commercially.

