Appendix A. Technical Detail and Supplemental Information Regarding
Statistical Procedures and Programs 39

Appendix B. Code Fragments..... 53

Appendix C. Reference Values/Toxicity Grades 56

Table of Abbreviations

| Abbreviation or Term | Definition/Explanation |
|----------------------|--|
| ACR | American College of Rheumatology |
| ANCOVA | Analysis of covariance |
| BMI | body mass index |
| BSA | body surface area |
| CDAI | Clinical Disease Activity Index |
| CMH | Cochran Mantel Haenszel |
| CRP | C-reactive protein |
| DAS28-CRP | Disease Activity Score (28 Joints) using CRP |
| DAPSA | Disease Activity index for Psoriatic Arthritis |
| DMARD | Disease Modifying Anti-rheumatic Drug |
| EOS | End of Study |
| ES | Erosion Score |
| ET | Early Termination |
| HAQ-DI | Health Assessment Questionnaire Disability Index |
| ICH | International Conference on Harmonisation |
| IP | Investigational product |
| IPD | Important protocol deviation |
| ITT | Intent-to-treat |
| JSN | Joint Space Narrowing |
| LOCF | Last observation carried forward |
| LDI | Leeds Dactylitis Index |
| MDA | minimal disease activity |
| mNAPSI | Modified Nail Psoriasis Severity Index |
| mTSS | van der Heijde modified Total Sharp Score |
| MI | Multiple imputation |
| NRI | Non-responder imputation |
| PASDAS | Psoriatic Arthritis Disease Activity Score |
| PRO | patient reported outcome |
| PsA | psoriatic arthritis |
| QW | Weekly |
| SAP | statistical analysis plan |
| SDAI | Simplified Disease Activity Index |
| SF-36 v2 | Medical Outcomes Health Survey Short Form 36 items version 2 |

| Abbreviation or Term | Definition/Explanation |
|-----------------------------|---|
| SPARCC | Spondyloarthritis Research Consortium of Canada |
| sPGA | Static Physician Global Assessment |
| TNF | tumor necrosis factor |
| VAS | visual analog scale |
| VLDA | Very Low Disease Activity |

1. Introduction

The purpose of this statistical analysis plan (SAP) is to provide details of the statistical analyses that have been outlined within the protocol amendment 3 for etanercept Study 20130207 dated 31 August 2016. The scope of this plan includes the final analysis that is planned and will be executed by the Biostatistics department unless otherwise specified.

2. Objectives

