Disease Activity index for Psoriatic Arthritis (DAPSA) (range 0-164)

DAPSA will be calculated based on the number of tender (TEN68) and swollen (SW66) joints, patient global assessment on a 0-10 scale (PtGA), patient global assessment of pain on a 0-10 scale (PtGAJP) and CRP in mg/dL. Since PtGA and PtGAJP are collected on a 0-100 scale, the formula has been modified to convert these scores to a 0-10 scale as such:

$$DAPSA = SW66 + TEN68 + PtGA/10 + PtGAJP/10 + CRP$$

If one or more components are missing in the formula, then DAPSA is set to be missing.

Leeds Enthesitis Index

The Leeds enthesitis index will be used for the PASDAS derivation only and will be calculated based on the following entheses:

| Entheses | Tenderness (0=Not Tender, 1= Tender) |
|--|--------------------------------------|
| Medial femoral condyle (left) | 0 or 1 |
| Medial femoral condyle (right) | 0 or 1 |
| Lateral epicondyle (left) | 0 or 1 |
| Lateral epicondyle (right) | 0 or 1 |
| Achilles tendon into calcaneum (left) | 0 or 1 |
| Achilles tendon into calcaneum (right) | 0 or 1 |
| Total Leeds Enthesitis Index | sum (range 0-6) |

If one or more components are missing, then enthesitis index is set to be missing.

SPARCC enthesitis index

SPARCC enthesitis index will be calculated based on the following entheses:

| Entheses | Tenderness (0=Not Tender, 1= Tender) |
|---|---|
| Medial epicondyle (left) | 0 or 1 |
| Medial epicondyle (right) | 0 or 1 |
| Lateral epicondyle (left) | 0 or 1 |
| Lateral epicondyle (right) | 0 or 1 |
| Supraspinatus (left) | 0 or 1 |
| Supraspinatus (right) | 0 or 1 |
| Greater trochanter (left) | 0 or 1 |
| Greater trochanter (right) | 0 or 1 |
| Quads into superior patella (left) | 0 or 1 |
| Quads into superior patella (right) | 0 or 1 |
| Max {Patella ligament into inferior patella (left), Patella ligament into tibial tubercle (left)} | 0 or 1 |
| Max{Patella ligament into inferior patella (right), Patella ligament into tibial tubercle (right)} | 0 or 1 |
| Achilles tendon into calcaneum (left) | 0 or 1 |
| Achilles tendon into calcaneum (right) | 0 or 1 |
| Plantar fascia into calcaneum (left) | 0 or 1 |
| Plantar fascia into calcaneum (right) | 0 or 1 |
| Total SPARCC Enthesitis Index | sum (range 0-16) |

If one or more components are missing, then SPARCC is set to be missing.

HAQ-DI

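### PASDAS needs two enthesitis sites that the protocol's only scheduled enthesitis examination omits; check the eCRF and settle the derivation before unblinding

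*SAP*

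**What the plan says.** **Endpoint.** Protocol Section 10.1.1.3 lists "Psoriatic Arthritis Disease Activity Score (PASDAS) at all measured timepoints" among the other secondary endpoints. SAP Section 4.1.3 adds change from baseline, and SAP Section 10.5.2 selects the week-24 change for comparison of each etanercept arm with methotrexate.

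**Derivation.** SAP Section 6.6 and Appendix A make the Leeds enthesitis index, scored 0 to 6, one of the PASDAS inputs. Appendix A says of it: "The Leeds enthesitis index will be used for the PASDAS derivation only and will be calculated based on the following entheses". The sites are the lateral epicondyle, medial femoral condyle and Achilles insertion, left and right.

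**Data collection.** The one enthesitis row in Protocol Table 1 is "Spondyloarthritis Research Consortium of Canada (SPARCC) Enthesitis Index". Protocol Section 7.3.8.3 says "The SPARCC enthesitis index assesses enthesitis at 18 sites with a resultant score of 0 to 16" and names the sites: "Enteses assessed are left and right medial and lateral epicondyles, supraspinatus insertion into greater tuberosity of humerus, greater trochanter". The list continues with the quadriceps insertion, inferior patellar pole, tibial tubercle, Achilles insertion and plantar fascia.

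**Missing inputs.** Under Appendix A, a single unscored site leaves the Leeds index missing, and a single absent input leaves PASDAS missing. SAP Section 9.3.1 does not impute baselines.

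**The concern.** The analysis calls for two sites that the protocol does not ask anyone to examine, and the SAP's rules leave no way round the gap. A programmer working only from these documents would produce an empty PASDAS table.

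If that came to light after unblinding, the choice would be between dropping a listed secondary endpoint and devising an unplanned formula with the treatment codes known. The second course would be hard to defend, even for a descriptive result.

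**Working it through.** No sample-size or error-rate arithmetic applies. The check is a count and a comparison of site lists.

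**1. Reproduce the protocol's own SPARCC figures.** Section 7.3.8.3 names nine entheses, each on both sides: medial epicondyle, lateral epicondyle, supraspinatus, greater trochanter, quadriceps insertion, inferior patellar pole, tibial tubercle, Achilles, plantar fascia.
- Sites: 9 × 2 = 18, the stated number.
- Maximum score: inferior pole and tibial tubercle together score at most 1 per side, so 18 − 2 = 16, the stated maximum.

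The named sites account for the whole total, so no unlisted site is hidden in it. The SPARCC table in SAP Appendix A also has no femoral condyle.

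**2. Match the six Leeds sites to those 18.**

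| Leeds site (SAP Appendix A) | In Protocol 7.3.8.3? |
|---|---|
| Lateral epicondyle, left and right | Yes (2) |
| Achilles insertion, left and right | Yes (2) |
| Medial femoral condyle, left and right | No (2) |

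Overlap is 4 of 6, and 2 of 6 have no scheduled source.

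**3. Look for a substitute elsewhere.**
- The SPARCC medial epicondyle is a different item: Appendix A lists it in the SPARCC table and the medial femoral condyle in the Leeds table.
- Knee tenderness in the 68-joint count is a joint finding, and the SAP does not map it to an enthesis.
- The only Leeds instrument in the protocol is the dactylitis index.
- The other PASDAS inputs (both global assessments, SF-36, joint counts, digit tenderness, CRP) are all scheduled at weeks 0, 12, 24, 36 and 48. The enthesitis input is the only one with a gap.

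**4. Apply the missing-data rules to protocol-specified data alone.** Two sites absent → Leeds index missing → PASDAS missing, at baseline and every later visit. The SAP prorates joint counts and tolerates up to two missing HAQ-DI categories, but gives the Leeds index no such allowance. Carrying forward a last value for rescued subjects cannot help, because there is no earlier value to carry.

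Result: 0 of 840 planned subjects have a PASDAS value at any of the five visits, if the condyles were not recorded.

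**5. Check the spread to other endpoints.** MDA and VLDA use the SPARCC index, and ACR 20 has no enthesitis component. The primary and key secondary tests, the gatekeeping procedure and the sample size are untouched. The SAP 10.5.2 list has twelve entries, and PASDAS is the only one that uses the Leeds enthesitis index.

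**The case against.** The strongest reply is that a gap in the protocol's description does not show a gap in the data. PASDAS is a protocol endpoint. The SAP describes itself as detailing analyses "outlined within the protocol amendment 3 for etanercept Study 20130207 dated 31 August 2016", and it tabulates each condyle as a 0/1 item, which is compatible with such fields existing on the eCRF. Protocol Section 7.2 sends the reader elsewhere for detail: "Refer to the applicable supplemental central laboratory, IXRS, IPIM, and study manuals for detailed collection and handling procedures". Those manuals and the eCRF are not available here, and the code in SAP Appendix B is redacted.

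That reply stands as far as it goes. A reader might infer that PASDAS was never collectable and the endpoint is already lost. The documents do not support that, and nothing should be read into the redaction. Nor do they show that the condyles were captured.

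It is also fair to say that the stakes are limited: one of twelve selected analyses, with a p-value that the SAP treats as descriptive. The silence of SAP Section 11 adds little, because the visible protocol gives no PASDAS formula from which the SAP could have departed.

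What the reply does not remove is the contradiction itself. Neither document says where the condyle scores come from, and the any-missing rules leave no alternative.

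**Conclusion.** The point holds as an inconsistency between the protocol's data collection and the SAP's derivation. It is certain that 2 of the 6 sites required for PASDAS are outside the protocol's scheduled examination and that, taken literally, the two documents yield no PASDAS value.

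Whether any data are lost is a yes/no question that only the eCRF can answer. If the condyles were captured, no value is lost for this reason and only the texts need reconciling. If they were not, PASDAS is missing for everyone. High confidence attaches to the mismatch alone.

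The point does not question the choice of PASDAS or of the Leeds index, and it has no bearing on the confirmatory conclusions. It still deserves action, because the check is cheap and any replacement rule is credible only if fixed before the treatment codes are known.

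**What to change.** Before unblinding, check whether the eCRF had fields for left and right medial femoral condyle tenderness.

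- **If it did:** state that data source in SAP Appendix A, and keep the six-site index and its any-missing rule. Align Protocol Section 7.3.8.3 and Table 1 at the next amendment, if there is one. An amendment for this alone is not warranted, since under Protocol Section 12.1 "The IRB/IEC must be informed of all amendments and give approval".
- **If it did not:** before unblinding, replace the Leeds input in SAP Appendix A with a single enthesitis input built only from collected sites. The sponsor should choose and justify it, apply it to all arms and visits, label the score 'modified PASDAS' and record the change in SAP Section 11. Otherwise, state that PASDAS cannot be derived and remove it from the Section 10.5.2 test list.

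The cost is one eCRF check and a few sentences of SAP text. The downside of the second branch is that a modified PASDAS is not the standard score and cannot be compared directly with PASDAS in other trials. The report should say so.

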The SF-36 v2 is a 36-item instrument that measures general health status and will be scored using the Quality Metric Health Outcomes Scoring Software. It includes 8 multi-item scales, each of which assesses one of the following 8 health concepts over the previous month: 1) limitations in physical activities because of health problems; 2) limitations in social activities because of physical or emotional problems; 3) limitations in usual role activities because of physical health problems; 4) bodily pain; 5) general mental health (psychological distress and well-being); 6) limitations in usual role activities because of emotional problems; 7) vitality (energy and fatigue); and 8) general health perceptions. SF-36 v2 includes the Physical Component Summary and Mental Component Summary measures. A higher score represents less disability.

Minimal Disease Activity (MDA)

A measure of low disease activity specific for PsA that incorporates measures of joint and enthesal inflammation, skin disease, PROs and functional disability to assess the subject's disease activity. Subjects are classified as achieving MDA if they fulfill 5 of the following 7 outcome measures:

- Tender joint count (0-68) ≤ 1
- Swollen joint count (0-66) ≤ 1
- Body Surface Area (BSA) ≤ 3
- Patient global assessment of joint pain (0-100) ≤ 15
- Patient global assessment of disease activity VAS (0-100) ≤ 20
- HAQ-DI (0-3) ≤ 0.5
- SPARCC enthesitis index ≤ 1

Details of the scoring algorithm are described in [Appendix A](#).

Modified Nail Psoriasis Severity Index (mNAPSI)

The modified NAPSI scale is an objective, numeric, and reproducible grading system for nail psoriasis that incorporates the following 7 clinical features:

- pitting (scores 0-3, depending on the number of pits)
- nail plate crumbling (scores 0-3, depending on the % of nail involvement)
- onycholysis and oil drop dyschromia (scores 0-3, depending on the % of nail involvement)
- leukonychia (0 = absent, 1 = present)
- red spots in lunula (0 = absent, 1 = present)

- nail bed hyperkeratosis (0 = absent, 1 = present)
- splinter hemorrhages (0 = absent, 1 = present)

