9.3.2 Missing Post-baseline Evaluation

Subjects with missing post-baseline efficacy data will be imputed as non-responder, ie, non-responder imputation (NRI) for the primary analysis of primary and key secondary efficacy endpoints (ACR 20 and MDA). Data will also be analyzed using multiple imputation (MI) as sensitivity analyses for primary and key secondary endpoints (ACR20 and MDA).

For analyses of other efficacy endpoints after week 24, data from subjects who remain in the double-blind period will be analyzed as observed with no imputation for missing data. Data from subjects who enter open-label rescue therapy will be imputed using last observation carried forward (LOCF).

For non-radiograph exploratory endpoints, data will be analyzed as observed without imputation for missing data.

For radiographic exploratory endpoints, data will be analyzed as observed with no imputation for missing data or for subjects who enter rescue treatment. In addition, data will be analyzed using LOCF imputation for missing radiographs and for subjects who enter rescue treatment as sensitivity analysis.

Baseline data will not be carried forward to any missing post-baseline value unless otherwise specified.

Missing post-baseline safety data will not be imputed.

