| Week 12 | 85 | Study Day 2 to 126 | 124 |
| Week 24 | 169 | Study Day 127 to 210 | 84 |
| Week 36 | 253 | Study Day 211 to 294 | 84 |
| Week 48 | 337 | >=Study Day 295 | n/a |

For the rest of the endpoints of interest, use the following window:

| Visit Week | Target Day | Window Definition | Interval (days) |
|-----------------------|------------|--|-----------------|
| Baseline ^a | 1 | Last Evaluation prior to or on Study Day 1 | n/a |
| Week 4 | 29 | Study Day 2 to 42 | 41 |
| Week 8 | 57 | Study Day 43 to 70 | 28 |
| Week 12 | 85 | Study Day 71 to 98 | 28 |
| Week 16 | 113 | Study Day 99 to 140 | 42 |
| Week 24 | 169 | Study Day 141 to 210 | 70 |
| Week 36 | 253 | Study Day 211 to 294 | 84 |
| Week 48 | 337 | >=Study Day 295 | n/a |

^a For swollen joint count and tender joint count, the baseline values are the values taken on the day of randomization before the first dose of investigational product.

Scoring Algorithms for Efficacy Endpoints

ACR Responder

The ACR response is a composite endpoint that classifies a patient as a responder or non-responder based upon improvement from baseline as defined by 7 endpoints. To be considered an ACR 20/50/70 responder, a subject must experience the following:

- At least 20/50/70% improvement in tender joint count (68 joints), AND
- At least 20/50/70% improvement in swollen joint count (66 joints), AND
- At least 20/50/70% improvement in 3 of the 5 following endpoints:
 - Physician global assessment (PhGA)
 - Patient global assessment (PtGA)
 - Patient global assessment of joint pain
 - Functional disability (HAQ-DI)
 - Acute phase reactant (CRP)

If joint data are partially missing, the joint counts will be prorated prior to deriving ACR responses. There is no imputation for missing secondary individual components (ie, HAQ-DI, CRP or ESR, pain VAS, PtGA, and PhGA).

In the case that some ACR components are missing, the ACR scores will be based on the non-missing components. If a subject's non-missing components are not sufficient to determine ACR response, then that subject will be considered as missing ACR response. The corresponding algorithm is listed below (using ACR 20 as an example):

1. If either swollen or tender joint counts is not improved at least 20%, the subject is an ACR non-responder
2. If both tender and swollen joint counts are improved at least 20%, and
 - a. If 3 or more of the other 5 ACR components are improved at least 20%, the subject is an ACR 20 responder;

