 - b. If 3 or more of the other 5 ACR components are not improved at least 20%, the subject is an ACR 20 non-responder;
 - c. If none of the above, the ACR response for the subject cannot be determined due to missing data and is therefore set to missing.
3. If the percent improvement of either swollen or tender joint counts is missing, and
 - a. If 3 or more of the other 5 ACR components are not improved at least 20%, the subject is an ACR 20 non-responder;
 - b. Otherwise, the ACR response for the subject cannot be determined due to missing data and is therefore set to missing.

Clinical Disease Activity (CDAI)

CDAI will be calculated based on the number of tender (TEN28) and swollen (SW28) joint using a 28-joint count, physician global assessment on a 0-10 scale (PhGA), and patient global assessment on a 0-10 scale (PtGA). Since PhGA and PtGA are collected on a 0-100 scale, the formula has been modified to convert these scores to a 0-10 scale as such:

$$CDAI = SW28 + TEN28 + PhGA/10 + PtGA/10$$

If one or more components are missing in the formula, then CDAI is set to be missing.

Leeds Dactylitis Index (LDI)

The Leeds Dactylitis Index (LDI) will be calculated based on the tenderness and circumference of dactylitic digits. First, identify involved digit (A) as a digit with tenderness score greater than 0. Second, identify control digit (B) as in the following scenarios:

1. contralateral digit (the digit on opposite hand and foot) if tenderness score associated with contralateral digit is 0.
2. If the tenderness score for contralateral digit is also greater than 0, then control digit is the digit listed in standard reference table below.

Note in scenario 2), the contralateral digit is also an involved digit (A), look up its control digit from standard reference table below.

For any digit with a missing tenderness score, it will be removed from LDI calculation.

For any involved digit with contralateral digit circumference missing, only calculate LDI when both involved digit and its contralateral are tender (tenderness score > 0). In latter case, refer to standard reference table in the same fashion as in scenario 2 above.

To calculate LDI for (A), take the ratio of circumference in mm of the involved digit (A) and control digit (B) . If the ratio difference $[(A/B)-1]$ is greater than 10%, multiply 100 and the ratio difference $[(A/B)-1]$ by the tenderness score corresponding to involved digit (A): :

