The HAQ-DI is the disability assessment component of the HAQ that assesses a patient's level of functional ability. It is calculated based on the mean score from the following eight categories: dressing & grooming, rising, eating, walking, hygiene, reach, grip, and usual activities. Each category is comprised of two or three questions that are scored as 0 (without any difficulty), 1 (with some difficulty), 2 (with much difficulty), or 3 (unable to do). The highest score for questions in each category (range 0 to 3)

determines the score for the category, unless aids or devices are required. Dependence on equipment or physical assistance increases a lower score (ie, scores of 0 or 1) to the level of 2 to more accurately represent underlying disability. If the subject's highest score is a 3 then it stays a 3. Devices and aids are assigned to the categories as follows:

| HAQ-DI Category | Companion AIDS OR DEVICES item |
|---------------------|--|
| DRESSING & GROOMING | Devices used for dressing (button hook, zipper pull, long-handled shoe horn, etc.) |
| ARISING | Built up or special chair |
| EATING | Built up or special utensils |
| WALKING | Cane, walker, crutches, wheelchair |
| HYGIENE | Raised toilet seat, bathtub seat, bathtub bar, long-handled appliances in bathroom |
| REACH | Long-handled appliances for reach |
| GRIP | Jar opener (for jars previously opened) |

The eight category scores are averaged into an overall HAQ-DI score on a scale from 0 (no disability) to 3 (completely disabled) when 6 or more categories are non-missing. If more than 2 categories are missing, the HAQ-DI score is set to missing.

Minimal Disease Activity (MDA)

MDA response will be derived based on the following criteria:

| Outcome | Criteria |
|---|----------|
| Tender joint count (0-68) | ≤ 1 |
| Swollen joint count (0-66) | ≤ 1 |
| Body surface area (0-100) | ≤ 3 |
| Patient global assessment of joint pain – PTGAJP (0-100) (used for patient pain VAS) | ≤ 15 |
| Patient global assessment of disease activity – PTGA (0-100) (used for patient global disease activity VAS) | ≤ 20 |
| HAQ-DI (0-3) (used for HAQ) | ≤ 0.5 |
| SPARCC enthesitis index (0-16) (used for tender enthesesal points) | ≤ 1 |

Use prorated scores for Tender and Swollen joint count. If 5 of 7 criteria are met then the subject has achieved MDA response.

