If all components are missing, then MDA is set to be missing. If one or more but not all components are missing in the formula, then MDA is set to be zero.

Very Low Disease Activity (VLDA)

VLDA response will be derived based on the following criteria:

| Outcome | Criteria |
|--|----------|
| Tender joint count (0-68) | ≤ 1 |
| Swollen joint count (0-66) | ≤ 1 |
| Body surface area (0-100) | ≤ 3 |
| Patient global assessment of joint pain (0-100) (used for patient pain VAS) | ≤ 15 |
| Patient global assessment of disease activity (0-100) (used for patient global disease activity VAS) | ≤ 20 |
| HAQ-DI (0-3) (used for HAQ) | ≤ 0.5 |
| SPARCC enthesitis index (0-16) (used for tender enthesial points) | ≤ 1 |

Use prorated scores for Tender and Swollen joint count. If all 7 criteria are met then the subject has achieved VLDA response. If all components are missing, then VLDA is set to be missing. If one or more but not all components are missing in the formula, then VLDA is set to be zero.

mNAPSI

The modified NAPSI will be calculated for all fingernails at baseline. For remaining visits, the modified NAPSI will only be calculated for the worst fingernail (ie, the fingernail with the highest score) based on the baseline assessment. The total score will range from 0-13 as follows:

| Clinical feature | Score |
|--|------------------|
| Pitting (0-3 based on severity)* | 0, 1, 2 or 3 |
| Nail plate crumbling (0-3 based on severity)* | 0, 1, 2 or 3 |
| Onycholysis and oil drop dyschromia (0-3 based on severity)* | 0, 1, 2 or 3 |
| Leukonychia (0=absent, 1=present) | 0 or 1 |
| Red spots in lunula (0=absent, 1=present) | 0 or 1 |
| Nail bed hyperkeratosis (0=absent, 1=present) | 0 or 1 |
| Splinter hemorrhages (0=absent, 1=present) | 0 or 1 |
| Total mNAPSI Score | sum (range 0-13) |

| Severity Codes | | | | |
|-------------------------------------|----------------|---------|---------|---------|
| Clinical feature | Score=0 | Score=1 | Score=2 | Score=3 |
| Pitting | no pits | 1-10 | 11-49 | ≥50 |
| Nail plate crumbling | no crumbling | 1-25% | 26-50% | >50% |
| Onycholysis and oil drop dyschromia | no onycholysis | 1-10% | 11-30% | >30% |

If one or more components are missing, then mNAPSI is set to be missing.

PASDAS

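### The MDA missing-component rule scores certain responders as failures when one or two of the seven components are missing

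*SAP*

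**What the plan says.** SAP section 6.6 defines the endpoint: "Subjects are classified as achieving MDA if they fulfill 5 of the following 7 outcome measures". The MDA entry in Appendix A repeats it: "If 5 of 7 criteria are met then the subject has achieved MDA response". Neither sentence requires all seven components to be observed.

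Appendix A then treats missing components in two steps. If all seven are missing, MDA is missing. Otherwise: "If one or more but not all components are missing in the formula, then MDA is set to be zero".

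The VLDA entry has the same sentence, "If one or more but not all components are missing in the formula, then VLDA is set to be zero", but a different threshold: "If all 7 criteria are met then the subject has achieved VLDA response".

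The ACR entry takes another approach: "In the case that some ACR components are missing, the ACR scores will be based on the non-missing components". It calls non-response from partial data only when that is settled, for example "If 3 or more of the other 5 ACR components are not improved at least 20%, the subject is an ACR 20 non-responder", and sets the response to missing when the observed components cannot decide.

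SAP section 9.3.2 gives the general rule for the primary analysis of ACR 20 and MDA: "Subjects with missing post-baseline efficacy data will be imputed as non-responder". It adds multiple imputation as a sensitivity analysis.

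**The concern.** The five-of-seven definition and the zero rule contradict each other for a subject with one or two components missing and at least five observed criteria met. No value of the missing components can undo that response, but the zero rule records a failure.

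The sentence is harmless for VLDA. All seven criteria are needed there, so a missing component always leaves the response unproven. MDA has two criteria to spare, and the sentence does not carry over.

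MDA at week 24 is in the alpha-controlled chain. Within each path it is tested after ACR 20, and rejecting it completes the path and releases 0.025 to the other comparison. Equal loss of responders across arms costs power. Unequal loss can bias the comparison in either direction.

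The multiple-imputation analysis may not show the problem, because partly missing MDA has become a zero and is no longer missing. If imputation works on the derived endpoint, a subject with nothing observed could be imputed as a responder, while one meeting six of six observed criteria stays a failure. The program code is redacted, so the level of imputation cannot be confirmed.

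**Working it through.** **1. Which patterns are affected.** Each component is met, not met or missing. A subject is a certain responder if at least five observed criteria are met, and a certain non-responder if observed-met plus missing is below five (at least three observed not met). Counting all patterns:

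| Missing | Patterns | Certain responder | Certain non-responder | Undetermined |
|---|---|---|---|---|
| 1 | 448 | 49 | 294 | 105 |
| 2 | 672 | 21 | 336 | 315 |
| 3 | 560 | 0 | 175 | 385 |
| 4 | 280 | 0 | 35 | 245 |

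With three or more missing, at most four criteria can be seen to be met, so no certain responder exists. The rule scores all 49 + 21 = 70 certain-responder patterns as zero. These are patterns, not patients.

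**2. Share of true responders who remain certain.** Assume each component is equally likely to be the missing one.

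| Criteria truly met | 1 missing | 2 missing |
|---|---|---|
| 5 | 2/7 | 1/21 |
| 6 | 7/7 | 6/21 |
| 7 | 7/7 | 21/21 |

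**3. The plan's own power figure.** Inputs from SAP section 3.2: MDA rates 15% (methotrexate), 30% (etanercept) and 35% (combination), 280 per arm, 10% dropout, two-sided alpha 0.025, so z = 2.2414. Formula:

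power = Φ[(d − z·s0)/s1], where d = p1 − p0, s0 = √(2·p̄(1 − p̄)/n) and s1 = √((p0(1 − p0) + p1(1 − p1))/n).

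For 15% vs 30% with n = 280: d = 0.15, s0 = 0.03529, s1 = 0.03472, giving Φ(2.042) = 97.9%. With n = 252 (280 × 0.9) it is 96.6%. For 15% vs 35% it exceeds 99.8% at both sizes. The stated power above 90% is reproduced.

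**4. Effect of the rule.** Under non-responder imputation, dropouts stay in the denominator. The starting rates are therefore 0.30 × 0.9 = 27%, 0.15 × 0.9 = 13.5% and 0.35 × 0.9 = 31.5%, with n = 280. Let m be the share of subjects with exactly one component missing, equal across arms. **m is an assumption.**

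- Under the rule, each rate is multiplied by (1 − m).
- With the fix, the multiplier is (1 − 5m/7) if every responder meets exactly five criteria, and 1 if every responder meets six or seven.

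For m = 5% under the rule: 25.65% vs 12.825%, d = 0.12825, s0 = 0.03331, s1 = 0.03287, giving Φ(1.630) = 94.8%.

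| m | Etanercept vs methotrexate: rule | With fix |
|---|---|---|
| 0 | 96.1% | 96.1% |
| 1% | 95.8% | 95.9–96.1% |
| 2% | 95.6% | 95.7–96.1% |
| 5% | 94.8% | 95.2–96.1% |
| 10% | 93.3% | 94.2–96.1% |
| 20% | 89.3% | 91.8–96.1% |

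Power reaches 90% at m = 18.4% under the rule, and not before 25.8% with the fix. For the combination arm at m = 20%, power is 98.7% under the rule and 99.2–99.8% with the fix.

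Known responders lost at m = 5%: 27 × 0.05 × (2/7 to 1) = 0.39 to 1.35 points with etanercept, and 13.5 × 0.05 × (2/7 to 1) = 0.19 to 0.68 points with methotrexate. The 13.5-point difference shrinks by 0.19 to 0.68 points.

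**5. Unequal loss.** On the planned 30% and 15% with n = 280, zeroing 10% of responders in the etanercept arm only gives 27% − 15% = 12.0 points and 89.6% power. In the methotrexate arm only, it inflates the difference to 30% − 13.5% = 16.5 points.

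**The case against.** **The sentences may be meant in order.** If the five-of-seven test comes first and the zero rule takes only subjects not yet classified, no certain responder is lost. The redacted code might confirm this. But the text states neither an order nor an exception, whereas the ACR entry is an explicit numbered sequence. If this is the intent, it still has to be written down.

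**It may be strict non-responder imputation applied to components.** Section 9.3.2 refers to missing efficacy data, the rule is blind to treatment, and with equal missingness it is conservative. That supports failing subjects whose response is unknown. It does not require overriding a response that is already determined.

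**The effect is small, and the power figures depend on assumptions.** This stands. All seven components are scheduled at week 24, Protocol section 7 asks for a visit's procedures on one day, joint counts are prorated, and HAQ-DI tolerates two missing categories. Components are therefore not equally likely to be missing. SPARCC is the exposed one, because a single missing entry in the index voids it. The 18.4% crossing also depends on counting dropout as non-response. With 30% vs 15% taken directly, it is 26.6% at n = 280 and about 20.0% at n = 252. At m of 1% to 2% the cost is at most about 0.5 points of power.

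**Conclusion.** The concern holds as a minor error in the scoring of a key secondary endpoint. As written, the rule turns determined MDA responders into failures when one or two components are missing, and only then. This follows from the text and needs no assumption.

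The size does rest on assumptions: an unknown rate of partial missingness, equal across arms, one component missing per affected subject, and equally likely components for the lower bounds. At 5% missing, the cost against a corrected rule is 0.4 to 1.2 points of power for etanercept monotherapy. Power for the combination comparison hardly moves. The sample size remains adequate unless partial missingness is far higher than the visit design suggests.

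**What to change.** Replace the zero rule for MDA in SAP Appendix A with one parallel to the ACR algorithm:

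- responder if at least five observed criteria are met;
- non-responder if at least three observed criteria are not met;
- otherwise missing, which becomes non-response in the primary analysis and stays open to imputation in the multiple-imputation analysis.

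The VLDA sentence discards no known responder and need not change for this reason.

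As a small clarification, state that MDA and VLDA are derived only at weeks 4, 12, 24, 36 and 48. Protocol Table 1 schedules no BSA or SPARCC at weeks 8 and 16, but neither composite has its own window table, so on the text both fall to the default table, which includes those weeks. Not deriving MDA there is the natural reading, and MDA away from week 24 is descriptive only. If it were tabulated at those visits, the present rule would give 0% in every arm.

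The cost is about two sentences in Appendix A and a small change to the derivation program. No new data are needed.
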